11.10.3 Local Skin Reaction

Skin discoloration is expected due to the color of the drug product and is not an adverse reaction. For reactions such as local pain, itching or erythema, initial treatment may include cold pack, ibuprofen for pain and observation every 30 minutes times 2 and then hourly until \leq grade 1 and patient is comfortable.

For significant edema or lipodystrophy, treat with cold pack, elevation of injection site and observation every 30 minutes times 2 and then hourly until ≤ grade 1 or patient is comfortable and stable.

For severe reactions (≥ grade 3: ulceration or necrosis; severe tissue damage) operative intervention may be indicated, seek surgical consult.

11.10.4 Prolongation of QTc Interval and Management

As of April 2019 there have been reports of three subjects with a QT prolongation present after a BMX-001 loading dose (28 mg/subject) that was not present at baseline. Prolongation of QTc interval has not been observed in preclinical studies of BMX-001.

In the BMX-HN-001 study, the prolonged QT interval presented in a subject at the 30 minute and 60 minute post-dose ECG.

In the BioMimetix Multiple Brain Metastases study, the prolonged QT interval presented in a subject at the 30 minute and 60 minute post-dose ECG.

In the BioMimetix Multiple Brain Metastases, the prolonged QT interval presented in a subject at the 60 minute post-dose ECG.

In all cases Electrocardiogram QT corrected interval prolonged did not exceed a grade 2 (average QTc 481 - 500 ms) according to CTCAE.

No action with regards to BMX-001 was taken due to these events and the subjects are continuing on the study and the QT prolongation appears to have resolved.

At the time of this protocol amendment, 40 subjects have received a loading dose of BMX-001 across 4 different trials. The percentage of subjects presenting with QTc prolongation after the loading dose equates to 7.5%. BioMimetix has reviewed all of the data for the subjects and there were no QTc prolongation outside of the three mentioned above.

If a subject develops prolonged QT after receiving a dose of BMX-001, the subject should be referred to cardiology for work up and the case should be reviewed with the BioMimetix Medical Monitor to determine further dosing of BMX-001 and inclusion in the study. Additionally, levels of electrolytes (potassium, calcium, and magnesium) should be checked and supplementation given to correct any values outside the normal range. Finally, concomitant therapies should be reviewed and adjusted as appropriate for medications with known QT-prolonging effects.

If the cause is not identified and the investigator believes it is appropriate, particularly if QTc remains elevated, study drug may be interrupted, and an ECG should be re-checked in approximately 1 week after the QTc prolongation was first observed or more frequently as clinically indicated. If QTc has recovered or improved and the investigator believes it is safe to do so, continuing BMX-001 therapy should be considered if previously held.

In any case, if a Grade 3 QTc interval (CTCAE) is identified, BMX-001 should be discontinued for that patient.

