11.5 Phase 1 Administration by Dose Escalation at levels below established MTD

The RP2D of BMX-001 has been established in a concluded Phase 1 trial with high-grade glioma patients. This head and neck cancer Phase 1 trial evaluated the two lower doses of BMX-001 and found no dose-limiting toxicities of BMX-001 in combination with cisplatin and also with radiation of the head and neck.

BMX-001 was administered subcutaneously as a loading dose before starting concurrent chemoradiation (days -4 through 0 depending on patient scheduling). After the loading dose, the maintenance dose levels were given two times per week for 8 weeks. The starting dose level was 7 mg loading dose. The BMX-001 dose was then escalated to 14 mg loading dose. After the loading dose, the BMX-001 maintenance dose was administered 7 mg twice a week.

The corresponding volumes of BMX-001, Injection Solution 10 mg/mL associated with the loading doses are as follows:

0.7 mL/subject loading dose = 7 mg/subject

1.4 mL/subject loading dose = 14 mg/subject

The corresponding maintenance doses would be equivalent to the following:

0.35 mL/subject maintenance dose = 3.5 mg/subject

0.7 mL/subject maintenance dose = 7 mg/subject

BMX-001 is administered by subcutaneous injection of a sterile 10 mg/mL solution in saline. The subcutaneous injections are at any optimum site on the torso, the upper leg or upper arm. Maintenance doses are approximately one-half the size of the loading dose and should be administered twice weekly. The first maintenance dose should be delivered either 3 or 4 days after the loading dose and subsequent maintenance doses delivered at 3 to 4 day intervals to average 2 doses per week.

Table – Dosing Levels for Groups I & II							
	Group I Group II						
Loading Dose	7 mg/Subject	14 mg/Subject					
Maintenance Dose							
1	3.5 mg	7 mg					
2	3.5 mg	7 mg					
3	3.5 mg	7 mg					
4	3.5 mg	7 mg					
5	3.5 mg	7 mg					
6	3.5 mg	7 mg					
7	3.5 mg	7 mg					
8	3.5 mg	7 mg					

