11.9 Dose Modifications

If adverse events occur that require holding BMX-001, the dose will remain the same once treatment resumes.

NCI CTCAE toxicity	BMX-001 dose
Hypotension	
≤ Grade 2	Maintain current dose. For grade 2
	may give IV fluids and place patient
	in Trandeleburg position.
≥ Grade 3	Discontinue BMX-001. Supportive
	care as below.
Injection site reaction	
≤ Grade 2	Administer acetaminophen 325-650
	mg PO 30 minutes prior to injection.
Intolerable grade 2	Hold drug until ≤ grade 1 then
_	resume. Supportive care as below.
≥ Grade 3	Discontinue BMX-001.

NCI CTCAE toxicity	BMX-001 dose
Other \geq grade 3 attributable to	Discontinue BMX-001.
BMX-001	
Electrocardiogram QT corrected	
interval prolonged	
Grade 1 (Average QTc 450 - 480 ms)	Maintain current dose.
Grade 2 (Average QTc 481 - 500 ms)	Hold BMX-001 pending review by
	sponsor. Refer to cardiology.
	ECG should be re-checked in
	approximately 1 week after the QTc
	prolongation was first observed or
	more frequently as clinically
	indicated.
Grade 3 (Average QTc >= 501 ms;	Discontinue BMX-001.
>60 ms change from baseline)	

Regardless of the reason for holding study drug treatment, the maximum allowable length of treatment interruption is 3 weeks.

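### Sections 11.9 and 11.10.4 give inconsistent dosing instructions for grade 2 QTc prolongation: one orders a hold pending review, the other states none

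*Combined protocol and SAP*

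**What the plan says.** **Section 11.9 (Dose Modifications).** The QTc row that begins "Grade 2 (Average QTc 481 - 500 ms" instructs the site: "Hold BMX-001 pending review by" the sponsor. It adds cardiology referral and a repeat ECG after about one week. Grade 1 keeps the current dose; grade 3 means discontinuation. Below the table, for holds of any cause, "the maximum allowable length of treatment interruption is 3 weeks".

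**Section 11.10.4 (Prolongation of QTc Interval and Management).** For a subject who develops a prolonged QT after a dose, with no grade given, the section asks for cardiology referral and says "the case should be reviewed with the BioMimetix Medical Monitor to determine further dosing of BMX-001 and inclusion in the study". Electrolytes and concomitant drugs are to be checked. On interruption it says: "If the cause is not identified and the investigator believes it is appropriate, particularly if QTc remains elevated, study drug may be interrupted". It continues that "an ECG should be re-checked in approximately 1 week after the QTc prolongation was first observed". Its only firm drug action is discontinuation at grade 3. Of the three earlier cases, all described as no worse than grade 2, it reports: "No action with regards to BMX-001 was taken due to these events".

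**Dosing schedule.** Section 11.5 states: "The first maintenance dose should be delivered either 3 or 4 days after the loading dose", with later doses also 3 to 4 days apart. Footnote h to the Section 13 table gives two doses a week in weeks 1 to 8. Section 11.6 sets the Phase 2 maintenance dose at 14 mg.

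**Which section takes precedence.** Section 13.2 names 11.9 for BMX-001 dose modifications. The opening of 11.10 calls for standard practice except where the text above it specifies otherwise.

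**The concern.** Both sections cover the same event, with the same cardiology referral and the same one-week repeat ECG. They differ on whether the next injection may be given. In 11.9 the answer at grade 2 is no until the sponsor has reviewed the case. In 11.10.4 the review decides further dosing, but nothing says what happens to a dose that falls due first, and no time limit is set for the review. Interruption depends on two conditions: no cause has been found, and the investigator thinks it appropriate. If a cause is found, such as a low electrolyte level, the interruption sentence does not apply at all, while 11.9 still requires the hold.

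That case is plausible here. Section 10.6 lists low magnesium and low potassium among the effects of cisplatin, and Section 6.2 treats hypokalemia as a risk factor for Torsades de Pointes. The week 4 ECG is taken after cisplatin has begun.

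At stake is repeat exposure, before review, in a subject with a QTc of 481-500 ms. Section 11.10.4 reports three prolongations after the 28 mg load, one of them in this study.

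**Working it through.** **1. The two rules compared for a QTc of 481-500 ms**

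| Step | 11.9 | 11.10.4 |
|---|---|---|
| Grade named | Grade 2 | None, except grade 3 for discontinuation |
| Cardiology referral | Yes | Yes |
| Review | Sponsor | Sponsor's Medical Monitor |
| Drug while review is open | Held | Not stated |
| Interruption | Mandatory | Optional, if no cause is found and the investigator agrees |
| Repeat ECG | About one week | About one week |

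The conflict lies in the fourth and fifth rows.

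**2. Whether another rule blocks the dose.** Section 13.2 bars re-treatment during a dose-limiting toxicity. Under 11.11.1 a non-hematologic DLT starts at grade 3, so that bar does not catch grade 2. What remains is the reference in 13.2 to 11.9, and so the hold exists only through 11.9.

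**3. Doses falling due before the repeat ECG.** Take the dose after which the prolongation is seen as day 0. The next dose is due on day 3 or 4, and the second one 3 or 4 days later:

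- 3 + 3: due on days 3 and 6
- 3 + 4: due on days 3 and 7
- 4 + 3: due on days 4 and 7
- 4 + 4: due on days 4 and 8

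Up to and including day 7, the first three schedules give 2 doses and the last gives 1. Strictly before day 7, the counts are 2, 1, 1 and 1. The range is 1 to 2 doses either way.

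Amount: 1 × 14 mg = 14 mg; 2 × 14 mg = 28 mg.

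**4. Cost of the hold.** Planned maintenance doses: 2 a week × 8 weeks = 16 (the eight rows of the 11.6 table are read as weeks, in line with footnote h). A one-week hold loses 1/16 = 6.3% to 2/16 = 12.5% of them. One week is within the three-week maximum.

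**The case against.** The strongest reply is that the protocol already settles the matter. Section 13.2 names 11.9, not 11.10.4, as the source of BMX-001 dose modifications. The opening of 11.10, the parent of 11.10.4, defers to what is specified above it, and 11.9 is the section directly above. A general permission to interrupt does not cancel a specific order to hold. Medical Monitor review before further dosing fits well with a pause, and 11.10.4 also speaks of resuming a drug that had been held.

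Most of this stands. On the better reading the hold exists, and the 1 to 2 doses are at risk only where a site acts on 11.10.4 alone. But 11.10.4 is where a site would look when a QTc result arrives. It is specific in its own right, never points back to 11.9, and makes optional what 11.9 makes mandatory. The cross-reference in 13.2 does not remove the conflicting text.

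Two smaller replies also have some force. The 3-to-4-day spacing comes from 11.5, which is headed Phase 1; however, twice-weekly dosing in footnote h implies much the same spacing. A maintenance-day ECG in week 1 (Section 13.1.4) may catch persistent prolongation before the one-week re-check, but 11.10.4 attaches no hold to that ECG below grade 3.

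A reader might infer from the report that no action was taken on BMX-001 that the 11.9 hold was breached in the three earlier cases. The documents do not support that. They do not say whether any case was actually grade 2, or whether the hold was in force at the time.

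**Conclusion.** The point holds as an inconsistency between two dosing instructions, not as a missing safeguard. The text of 11.10.4 is wrong as written because it conflicts with 11.9 at grade 2. Severity is minor to moderate: 11.9 should govern, but a site relying on 11.10.4 alone could give 1 to 2 maintenance doses (14 to 28 mg) that 11.9 forbids by the re-check at about one week. This rests on 3-to-4-day dosing in Phase 2 and on the review not being finished before the next dose is due. How many subjects would be affected cannot be derived, because the grades of the earlier cases are not given.

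A reader might also infer that the 7.5% in 11.10.4 understates the risk at the Phase 2 dose, since all three cases followed a 28 mg load. The documents do not establish this. The figure is correct (3/40 = 7.5%) and both of its parts are shown. The mix of loading doses among the 40 is not stated, and no decision rule uses the rate. The listing in 11.12 of QTc prolongation below 10% is not shown to be wrong.

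**What to change.** Amend 11.10.4 as follows:

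- State that at grade 2 (481-500 ms) BMX-001, including the next scheduled maintenance dose, is held until sponsor/Medical Monitor review is complete, as 11.9 requires, whether or not a cause has been found.
- Limit the discretionary interruption to grade 1. Because 11.9 keeps the current dose at grade 1, say that this is an investigator option alongside that row.
- State the grade to which each step applies, and refer to 11.9.
- Keep the cardiology referral, electrolyte check, medication review and repeat ECG.

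The cost is a few sentences in an amendment. Investigators lose the apparent freedom to continue at grade 2 before review, which 11.9 already denies them. A subject held for one week loses about 1 to 2 of the 16 maintenance doses.

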11.11 Dose-Limiting Toxicity (DLT)

Toxicities will be graded according to the NCI CTCAE version 4.03 criteria. DLTs will be defined as any of the following events that are at least (possibly, probably, or definitely) attributable to BMX-001 during the study. The DLT period includes from the start of BMX-001 through 4 weeks after CRT concludes.

A dose limiting toxicity is defined as an adverse event or laboratory abnormality that is: a) assessed as unrelated to disease progression, intercurrent illness, or concomitant medications; b) occurs during and/or following the first dose of BMX-001; and c) meets any of the following criteria:

11.11.1 Non-hematologic

The occurrence of non-hematologic grade 3 or greater adverse events considered to be possibly, probably, or definitely related to BMX-001 during treatment with BMX-001, excluding grade 3 alopecia and elevation in alkaline phosphatase, grade 3 nausea or vomiting unless occurring despite the use of standard anti-emetics.

> 14 day delay to re-treat due to failure to resolve any grade 3 or greater non-hematologic drugrelated toxicity to re-treatment criteria or pre-treatment baseline.

11.11.2 Hematologic

Occurrence of any of the following hematologic adverse events will be defined as DLT:

NCI CTCAE version 4.03 grade 3 febrile neutropenia or grade 4 neutropenia (ANC, including bands, ≤0.5 x 10⁹ /I);

- 2) NCI CTCAE version 4.03 grade 3 thrombocytopenia (platelet count of ≤ 50x10⁹/l);
- 3) > 14 day delay to re-treat due to failure to resolve hematologic toxicity to re-treatment criteria.
- 4) Grade ≥3 anemia

11.11.3 Other Considerations

Inability to complete 75% of the planned radiation dose.

Studies have been performed using intravenous infusions of a related metalloporphyrin in multiple models including rats, mice, dogs, guinea pigs, and baboons with the finding of doserelated hypotension [59]. Metalloporphyrin compounds being evaluated are potent, catalytic antioxidants and have the potential to scavenge superoxide within the vascular system and thereby change the balance of superoxide and nitric oxide in the microvasculature. This would augment the vasodilating activity of nitric oxide and lead to hypotension [59]. This has been found in animal models to be a significant, but transient side effect and, therefore, blood pressure monitoring is essential in this proposed clinical trial of a metalloporphyrin compound. Studies of rats, mice, and monkeys have been performed with BMX-001 and have shown transient, dose-related hypotension. Hypotension is related to plasma Cmax levels and subcutaneous administration significantly reduces the risk of this toxicity in mice and primates (unpublished data per BioMimetix JV, LLC). We have designed this protocol to monitor blood pressure closely. Preliminary data suggests that the dose-limiting toxicity will be local irritation at the subcutaneous injection site. This dose-limiting toxicity is expected to be related to the concentration of the administered drug and the volume administered rather than to subject body size.

Because of the development of transient hypotension in rat models, patients will undergo blood pressure monitoring before, during, and after the BMX-001 injections. In primate studies, the primary toxicity seen was skin reaction/irritation due to subcutaneous injection. Care will be taken to limit the volume of the injections to no more than 1.4 mL per site.

A summary of the possible adverse side effects that could be associated with BMX-001 administration is below. These possible side effects are dose-dependent, and the relatively low doses of this drug planned in this study have not been associated with side effects in animals other than those related to the color of the injected drug.

The most common side effects (expected to occur in more than 30% of subjects) are:

- Red to brown discoloration of the skin at the injection site which may take up to several weeks to resolve
- Irritation at the site of the injection of the drug under the skin
- Transient tachycardia from the study drug

Less common side effects (expected to occur in 10-30% of subjects) are:

- Transient pain at the site of the injections of the drug under the skin
- Local histamine release which could be caused by the study drug. This could cause
 pruritus (itching), erythema (redness), edema (swelling), urticaria (welts). This is
 expected to resolve within a couple of hours of injection

Rare side effects (expected to occur in less than 10% of subjects) are:

- Temporary hypotension (low blood pressure)
- Malaise or "not feeling well" for a few hours
- Prolongation of the QTc interval

An additional possible side effect is:

- Light-activated skin rash in response to sun exposure
- Red to dark color of urine
- It is also possible that previously unobserved and unexpected side effects could occur.

11.13 Risk Classification

The overall risk classification of this research is unknown. Clinical trials using BMX-001 in head and neck cancer patients have not been performed.

12 Other Therapy

12.1 Permitted Supportive Therapy

All supportive therapy for optimal medical care will be given during the study period at the discretion of the attending physician(s) within the parameters of the protocol and documented on each site's source documents as concomitant medication. These may include analgesics, antiemetics, topical mouth rinses (Viscous lidocaine is allowed), skin creams/ointments, topical anesthetic/solution for laryngoscopy, etc. The use of amifostine as a radioprotector is not allowed. The use of granulocyte colony-stimulating factor or erythropoietin is not allowed. Any exceptions must be approved by a Principal Investigator or representative from BioMimetix JV, LLC.

12.2 Prohibited Therapies

These are prohibited during the active study drug treatment period of the study and up until the first visit following completion of chemo therapy and radiation (~1 month).

- Low-level laser treatment for OM
- Amifostine (Ethyol®)
- Benzydamine hydrochloride
- Caphosol® or similar re-mineralizing solutions
- Cevimeline hydrochloride (Evoxac®)
- Glutamine applied topically
- GM-CSF applied topically
- IL-11 (Neumega®)
- 'Magic mouthwashes' or 'Miracle mouthwashes'
- Chlorhexidine
- Hydrogen peroxide rinses
- Tetracycline
- Any other listed disallowed medications
- MuGard™
- Nitrates, phosphodiesterase type 5 (PDE 5) inhibitors (e.g., sildanefil, tadalafil, or similar agents) or other drugs that in the judgment of the treating investigator could create a risk of a precipitous decrease in blood pressure are prohibited
- Palifermin (Kepivance®) or other keratinocyte or fibroblast growth factor
- Pilocarpine hydrochloride (Salagen®)
- Povidone-iodine rinses
- Steroid rinses
- Episil® spray
- Sucralfate in suspension form (use of sucralfate tablets is not proscribed)
- Other biologic response modifiers except systemic hematopoietic growth factors for the management of anemia or myelosuppression
- Concurrent approved or investigational anti-cancer therapy (e.g., chemotherapy, immunotherapy, targeted therapy, hormone, and biologic therapy) other than the Protocol regimen
- Other investigational agents

• Use of drugs known to lengthen QT intervals should be avoided or minimized.

13 Screening and On-Study Tests and Procedures

On-Study Tests and Procedures											
Evaluation	Screeninga	Base-	Wk 9 and								
		line ^a	1	2	3	4	5	6	7	8	Forward ^b
		Day									
		-4 to									
T.C. 1	37	0									
Informed consent	X	37	37	37	37	37	37	77	77	37	77
History and	X	X	X	X	X	X	X	X	X	X	X
physical exam ^b	37	37	37	X	37	37	37	37	37	37	37
Medications ^b	X X	X	X	X	X	X	X	X	X	X	X
Height		37	37	37	37	37	37	37	37	37	37
Weight ^b	X	X	X	X	X	X	X	X	X	X	X
Vital signs ^b	X	X	X	X	X	X	X	X	X	X	X
Blood pressure	X	X	X	X	X	X	X	X	X	X	
and heart rate ^c	37		37	37	37	37	37	37	37	37	37
CBC with	X		X	X	X	X	X	X	X	X	X
differential ^b CMP ^b	37		V	X	37	N/	V	V	V	37	V
PT/aPTT	X X		X	X	X	X	X	X	X	X	X
	X	Xj		1	1						
Serum beta-HCG ECG ^d	N/		V	1	1	37					
Mucositis ^b	X	X	X	X	X	X	X	X	X	X	X
(clinical score)	A	Λ	Λ	Λ	Λ	Λ	Λ	Λ	Λ	Λ	Λ
Saliva production ^e		X									X
(stimulated and		Λ									Λ
unstimulated)											
XeQoLs,		X								X	X
OMWQ-HN,		21								21	71
DLQI											
Questionnaires											
FACT-HN		X								X	X
Questionnaire,											
PRO-CTCAE HN											
Assessment of	X										X
measurable											
disease by											
imaging ^f											
Toxicity	X	Ongoing						X			
Assessment											
BMX-001g, h		X	X	X	X	X	X	X	X	X	
Cisplatin i			X	X	X	X	X	X	Xi		
Radiation		Daily Monday-Friday for 6-7 weeks ^k									

^a Screening evaluation should be done within 21 days of starting BMX-001. The screening evaluation and baseline evaluation may be combined. Informed consent may be done within 28 days of starting BMX-001.

b Study assessments for History and Physical, medications, weight, vital signs, CBC w/ diff, CMP, and mucositis will be obtained at screening, baseline, weekly during therapy, and following therapy at clinic visits in which timing is scheduled under standard of care. Screening CBC with diff and CMP prior to the first dose of Cisplatin need not be repeated on week one for chemotherapy naïve subjects per institutional practice. Study visits following therapy (Week 9 and forward) will be under SOC and at minimum will include study data collection for the CRF at a post-therapy visit within 1 month of completion of

radiation (or within 1 month of completion of BMX-001 treatment) and at 6 and 12 months post radiation \pm 1 month. Mucositis will be scored using the CTCAE version 4.03. Toxicity assessment will continue to be obtained during year 1 to identify late toxicities possibly related to SOC or with study drug. PT/aPTT will be measured once and can be done at either screening or baseline.

- ^c Blood pressure and heart rate will be measured pre-dose and then after 30 (\pm 5), 60 (\pm 5), 120 (\pm 10) minutes on the loading dose. It will be checked pre-dose, and post-dose at 30 (\pm 5), and 60 (\pm 5) minutes all other days of BMX-001 administration.
- ^d Phase 2: ECG will be done at screening and will also be done pre-dose as well as at 60 (± 15) minutes after dosing on the loading day and on a maintenance dose injection day during week 1 and week 4, both pre and post dose at 60 (± 15) minutes.
- e Saliva production will be measured on baseline and the post-therapy measurement will be obtained at clinic visit within 1 month of the end of radiation therapy and at 6 and 12 months ± 1 month. If the post-therapy measurement cannot be obtained, this will not be considered a protocol deviation.
- f Assessment of measurable disease by imaging will be done according to SOC, i.e., during screening (up to 8 weeks prior to enrollment) and at approximately 3 and 12 months during follow-up. The 12-month (+/- 1-month post completion of radiation therapy or BMX-001 treatment) follow-up imaging for this study will be a chest x-ray and is required as part of this study protocol and is specifically for research purposes.
- g For BMX-001, Day -4 to 0 will be the loading dose.
- h For BMX-001, doses (50% of the loading dose) will be twice a week subcutaneously weeks 1-8.
- ⁱ Cisplatin 100mg/m² IV q21 days starting Day 1 for 2-3 doses or 30-40mg/m² IV per institutional standard each week of treatment x 6-7 total doses.
- ^j Female patients only: pregnancy test (serum beta-HCG) no more than 48 hours prior to first dose of BMX-001.
- ^k Radiation therapy may extend into week 8. This is allowable and there is no limitation for radiation therapy extending into the 8th week of BMX-001 treatment.

